
SPECIFIC AIMS

1. The first aim of this study is to confirm target engagement of cognitive control training at both the behavioral and neural levels of analysis in a clinical sample of patients reporting high levels of urgency. We predict that compared to the control group, patients completing cognitive training will show lower interference (improved behavioral performance) and decreased ERN and N2 amplitudes on a Stop-Signal response inhibition task.
2. The second aim is to examine clinical outcomes of cognitive control training. Based on Preliminary Study A, we predict that all patients receiving treatment at the BHP will report lower urgency scores at discharge; however, we predict that this decrease will be significantly greater in those receiving cognitive training. In addition, we predict that

participation in the training will be associated with greater reductions in depression symptoms, urges to engage in NSSI, and craving related to substance use.

3. The third aim is to assess this training's feasibility and acceptability to patients in a real-world clinical setting. We predict that at least 75% of enrolled patients will complete all training sessions.

SUBJECT SELECTION

This is a sub-study under the existing protocol entitled "Establishing the Effectiveness of Cognitive-Behavioral Partial Hospitalization for Anxiety, Depression, and Overall Functioning" (# 2010-P-001047/6). We will recruit 110 participants from the patient population at the McLean Hospital Behavioral Health Partial Hospital Program (BHP). Inclusion criteria include: (a) BHP patient, (b) score above a 3 on either the UPPS Negative Urgency Scale or the UPPS Positive Urgency Scale at admission, (c) able to complete a computer task for 15 minutes, and (d) consent to main BHP study protocol (# 2010-P-001047). Participants will be excluded from participation if they are experiencing acute symptoms of mania or psychosis; if they are currently undergoing ECT; or if they have a history of a traumatic brain injury. Participants who are left-handed will be excluded from the EEG portion of the study but will be allowed to complete all other portions of the study.

Additional inclusion criteria for the research study will be consistent with admission criteria for the BHP program. Specifically, patients who are acutely psychotic and are deemed unfit for admission at the BHP will not be invited to participate in this study.

SUBJECT ENROLLMENT

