Procedures under existing BHP protocol: Upon arrival to the Behavioral Health Partial Program, all patients will be oriented by the Community Residence Counselors and/or Nurse Practitioner (all CITI certified staff members) to the program, building and set-up of the treatment. Once oriented, patients will also be informed that as part of their treatment at the BHP they will be completing extensive self-report measures and a diagnostic interview. The research coordinator will explain to patients about our current research study examining the efficacy of CBT in naturalistic settings and asked whether or not they would like to consent to having their assessments be de-identified and included in our research database. It will also be explicitly instructed to patients, that if they were to refuse consent/participation, their treatment at the BHP will not be affected in any way. Patients will have the option to rescind their consent/participation at any point, and subsequently the Research Coordinator will take the appropriate measures to accommodate this decision.

Procedures under proposed protocol: The research coordinator or another member of the study staff will approach eligible patients (scoring above a 3 on either the Negative or Positive Urgency scale of the UPPS-P and consented to main BHP study) on their second or third day in the program and inform them about the study. Interested patients will then receive a detailed description of the study procedures, risk, and benefits and will sign an informed consent form.

Once enrolled, participants will be randomly assigned by a random number generator to one of two arms: treatment as usual + Cognitive Control Training (TAU+CCT), or treatment as usual (TAU). The PI or post-doctoral fellow will be responsible for randomization, and will notify the

Research Coordinator of each participant's assignment. Up to 20 participants will be assigned to the non-randomized pilot phase that will only include TAU+CCT, with no EEG session.

STUDY PROCEDURES

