Design overview. We will conduct a randomized controlled trial of computerized cognitive control training among patients admitted to the BHP who report elevated scores on the urgency scales. Prior to beginning the randomized phase, we will enroll up to 20 participants into a pilot phase that will include the training program and all measure described below, with the exception of the EEG task. Next, Up to 90 patients will be randomized, with the goal of at least 68 patients completing baseline and discharge measures of impulsivity, symptoms, and craving for substances; half of these participants will be randomized to active training while half will undergo treatment as usual in the BHP. Participants randomized to the active training condition will be asked to complete eight to ten sessions of computerized cognitive training that combines working memory training and response inhibition training. This is a sub-study under the existing protocol entitled "Establishing the Effectiveness of Cognitive-Behavioral Partial Hospitalization for Anxiety, Depression, and Overall Functioning" (# 2010-P-001047/6). Data obtained under the existing BHP protocol will be shared with Investigators from this study.

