**Date: 2/19/2021**

**NCT#: NCT03527550**

The statistical analysis plan for primary outcome measures is as follows:

1. Change in Average Score on Negative Urgency Scale:

*A 2 (condition: TAU, TAU + cognitive training) x 2 (time) repeated-measures Analysis of Variance (ANOVA) will be used to test change in negative urgency at time 1 (admission) and time 2 (discharge), and whether participants differ in their average change in negative urgency as a function of condition (interaction of condition X time).*

2. Change in Average Score on Positive Urgency Scale:

*A 2 (condition: TAU, TAU + cognitive training) x 2 (time) repeated-measures Analysis of Variance (ANOVA) will be used to test change in positive urgency at time 1 (admission) and time 2 (discharge), and whether participants differ in their average change in positive urgency as a function of condition (interaction of condition X time).*

Statistical Analysis Plan for Secondary Outcome Measures:

1. Change in Estimated Stop-Signal Reaction Time (SSRT) on Stop-Signal Task (ms):

*A 2 (condition: TAU, TAU + cognitive training) x 2 (time) repeated-measures Analysis of Variance (ANOVA) will be used to test change in SSRT at time 1 (admission) and time 2 (discharge), and whether participants differ in their average change in SSRT as a function of condition (interaction of condition X time).*

2. Feasibility of assessing change in event-related potentials (ERPs) during a Stop-Signal Task in a partial hospital population:

*This will be tested using descriptive statistics assessing the percentage of participants who are able to complete and provide ERP data for the stop-signal task.*

3. Completion Rates:

*This will be tested using descriptive statistics assessing the percentage of enrolled participants who complete the training intervention and the discharge session. This will be compared to an a priori benchmark of a 75% completion rate, based on previous studies.*

4. Average Perceived Helpfulness of Training

*This will be tested using descriptive statistics assessing the average rating of overall perceived helpfulness of the intervention, as rated by participants using a self-report form at the discharge session. This average rating will be compared to an a priori benchmark of an average rating of 4.0 or greater for each of the two training tasks (PASAT and Go/NoGo).*

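### The 75% training-completion benchmark is taken over all enrolled participants, about half of whom are never offered training, so the rate as worded is expected to peak at 50% to 59%

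*SAP*

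**What the plan says.** The SAP, under secondary outcome 3 (Completion Rates), reports the "percentage of enrolled participants who complete the training intervention and the discharge session" and sets it against a 75% benchmark attributed to previous studies. Aim 3 in the protocol's Specific Aims makes the matching prediction: "We predict that at least 75% of enrolled patients will complete all training sessions". The Hypothesis 4 analysis, under Biostatistical Analysis, again describes training completion as a percentage of those enrolled.

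The protocol also makes clear who is enrolled:

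- Subject Selection: "We will recruit 110 participants from the patient population".
- Subject Enrollment, randomised phase: "Once enrolled, participants will be randomly assigned by a random number generator to one of two arms".
- Subject Enrollment, pilot: "Up to 20 participants will be assigned to the non-randomized pilot phase that will only include TAU+CCT".
- Design overview: "Up to 90 patients will be randomized, with the goal of at least 68 patients completing baseline and discharge measures", and "half of these participants will be randomized to active training while half will undergo treatment as usual in the BHP".

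On the amount of training, the Design overview says that patients in the active arm "will be asked to complete eight to ten sessions of computerized cognitive training". The Cognitive Control Training section repeats the range of eight to ten, then says ten are requested and that five may be accepted when scheduling is difficult. The SAP gives no session count.

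**The concern.** A completion rate for an intervention should be taken over the people assigned to it. Here the stated denominator includes the TAU arm, whose members have no training to complete and can only count as non-completers. The 75% figure is the one numerical prediction attached to Aim 3. Applied as written, it would return a failing result whether the training was well tolerated or not, and so would say nothing about feasibility.

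Two related matters are also left open. Neither document says whether the non-randomised pilot patients, all of whom are trained, belong in the rate. And the number of sessions that makes a patient a completer is not fixed.

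**Working it through.** The 75% benchmark is set in advance with no calculation behind it, so there is no derived figure to reproduce. The planned numbers do reconcile: 20 pilot + 90 randomised = 110 recruited.

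**Inputs.** Pilot size P is up to 20, all trained (Subject Enrollment). Number randomised R is up to 90, half to training (Design overview). The benchmark is 75% (SAP secondary outcome 3; Aim 3).

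**Step 1: highest expected rate as worded.** Suppose the split is even and every trained patient completes. The rate is then (P + R/2) / (P + R).

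- Randomised patients only: 45/90 = 50.0%.
- Pilot of 10 (an illustrative value) plus 90 randomised: 55/100 = 55.0%.
- Full pilot of 20 plus 90 randomised: 65/110 = 59.1%.

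The SAP sentence also mentions the discharge session. If both conditions must be met, the rate can only be lower.

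**Step 2: what 75% would require.**

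- Randomised only: 0.75 × 90 = 67.5, so 68 completers, with 45 patients in training.
- With the full pilot: 0.75 × 110 = 82.5, so 83 completers, with 65 patients in training.

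Put another way, the training arm would have to receive 68 of the 90 randomised patients, or 83 − 20 = 63 of 90 with the pilot counted, and all of them would have to complete.

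**Step 3: does a smaller trial help?** Both numbers are upper limits, so R could be below 90. With a full pilot, (20 + R/2) / (20 + R) ≥ 0.75 gives 20 + 0.5R ≥ 15 + 0.75R, hence R ≤ 20. That is far short of the goal of at least 68 randomised patients completing their measures.

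**Step 4: how a true 75% would appear.** If exactly 75% of trained patients complete, the rate as worded has an expected value of 0.75 × 45/90 = 37.5% (randomised only) or 0.75 × 65/110 = 44.3% (full pilot).

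**Step 5: with the denominator corrected.** Over those randomised to training the maximum is 100%. Since 0.75 × 45 = 33.75, the benchmark is met by at least 34 of 45. If the pilot were pooled in, 0.75 × 65 = 48.75, so at least 49 of 65.

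**Session count.** Aim 3 requires every session; the training section requests ten, expects eight to ten and accepts as few as five. The documents give no figures on how many patients reach each count, so the effect of the choice on the rate cannot be calculated.

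**The case against.** The strongest reply is that nobody would analyse it this way. Aim 3 is about how feasible and acceptable the training is to patients, the Hypothesis 4 sentence pairs completion with satisfaction, and SAP outcome 4 asks for ratings of the two training tasks, which only trained patients can give. The restriction to trained patients may be implicit. As a prediction of what an analyst would do, this is probably right. But neither document says so, and the guess does not settle whether the denominator is 45 or 65.

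A second reply is that the SAP sentence, under a plural title, may intend two rates: training completion among those trained, and discharge-session completion among everyone enrolled. Both arms have a discharge assessment, and the SAP is dated later than the protocol, so the reading is possible. The plan for 68 of 90 to complete baseline and discharge measures is 75.6%, close to the benchmark, but the documents do not connect the two figures. This reading does not repair Aim 3 or Hypothesis 4, where training completion alone is taken over the enrolled, and the SAP still gives no separate denominator for training.

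A third reply concerns sessions. A reader might infer that the protocol contradicts itself and that the threshold could be picked to suit the result. The documents do not support that. The training section reads mostly as a hierarchy: ten requested, eight to ten expected, fewer tolerated when time is short, which fits an average stay of 8.5 days. The percentage of sessions completed is also a planned variable, so rates at other thresholds can be derived. What stands is a missing definition.

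**Conclusion.** The denominator is wrong as written, and consistently so in three places. At planned numbers the rate is expected to reach at most 50% (randomised only) or 59% (full pilot), against a benchmark of 75%. This assumes an even split and completion by every trained patient, the most favourable completion possible.

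Three stronger conclusions should be resisted. These are expected values, not hard ceilings: the protocol describes a random number generator and no blocking, so the arms need not be exactly equal. A reader might also infer that the trial will report its training as infeasible; the documents do not show that, because an analyst may well use the trained arm. Nor does the error reach the main results: the outcome is descriptive, no test or stopping decision hangs on it, and the primary urgency analyses and the sample size do not use it.

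The point is therefore minor but definite. The undefined session count is a secondary clarification.

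**What to change.** Reword SAP secondary outcome 3 so that training completion is the number completing training divided by all participants randomised to TAU plus cognitive training, compared with 75% (at least 34 of 45 at planned numbers). Report the non-randomised pilot separately. If attendance at the discharge session among all randomised patients is also of interest, report it as its own rate and state whether the 75% applies to it. State which session count makes a patient a completer, and do so before completion data are examined. Read Aim 3 and the Hypothesis 4 analysis in line with this definition.

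The cost is a few sentences of SAP wording. No new data are needed. The one trade-off is that a stricter session count may give a less favourable rate.
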